11.9.2. Analyses of Subgroup

Subgroup analyses of the primary efficacy endpoint using the ANCOVA model will be performed. Subgroups will include but not limited to, the subgroups outlined in Table 3.

Table 3: Planned Subgroup Analyses

[figure not shown]
Subgroup Name	Subgroup Levels
Region	North America, Europe, Asia-Pacific; All regions except Japan vs. Japan
Diabetes mellitus Status (at baseline)	Yes, No
Age (years)	< 30, ≥30 - ≤60, > 60
Sex	Male, Female
BMI (kg/m ²)	< 30, ≥ 30
Concomitant oral estrogen at screening	Yes, No
Dosing Group	Group 1: Oral estrogen intake (any age) or < 30 years old Group 2: ≥ 30 to ≤ 60 years old; no oral estrogen intake Group 3: > 60 years old; no oral estrogen intake

[figure not shown]
Statistical Analysis Plan
TCH-306EXT

Ascendis Pharma A/S
Page 25 of 31

The absolute values and mean change from baseline by visit will be presented with descriptive statistics for all treatment groups using the baseline extension period baseline. For subjects switched from syringe to auto-injector during the extension period, the following analysis will be repeated for the subjects who switched from syringe to auto-injector:

- Exposure/compliance
- TEAEs
- Injection site reaction
- Antibody (only positive vs negative)
- Device related PRO

11.11. SAFETY ANALYSIS

Unless otherwise specified, safety analyses will be performed using the Safety Analysis population for the extension period. The safety parameters will include adverse events (AEs), clinical laboratory, vital sign, electrocardiographic (ECG) parameters, MRI, fundoscopy, immunogenicity, and other safety parameters if collected. For safety endpoints, all analyses will be based on the observed data (i.e., with no imputation of missing data), unless otherwise stated. These summaries will be presented by treatment group in the extension period.

Adverse events will be coded by system organ class (SOC) and preferred term (PT) using the Medical Dictionary for Regulatory Activities (MedDRA) Version 26.0.

An extension period AE (classified by preferred term) will be considered as treatment emergent adverse event (TEAE) if it occurred on or after the first dose of open-label lonapegsomatropin and was not present prior to the first dose of open-label lonapegsomatropin, or it was present at the first dose of open-label lonapegsomatropin but increased in severity during the study through 14 days after the last dose of treatment on the extension period.

A TEAE that started on or after the first dose date of open-label lonapegsomatropin will be counted as extension period TEAE.

- Summary of TEAEs by treatment
- TEAEs by treatment, SOC and PT (sorted by descending frequency by SOC and PT)
- TEAEs by treatment, SOC and PT Reported by > 5% of subjects in any treatment group
- Related TEAE by treatment, SOC and PT
- Serious TEAEs by treatment, SOC and PT (sorted by descending frequency by SOC and PT)
- Serious Related TEAEs by treatment, SOC and PT (sorted by descending frequency by SOC and PT)
- AEs leading to death by treatment, SOC and PT (sorted by descending frequency by SOC and PT)
- TEAEs leading to discontinuation of study by treatment, SOC and PT (sorted by descending frequency by SOC and PT)
- TEAEs leading to discontinuation of treatment by treatment, SOC and PT (sorted by descending frequency by SOC and PT)
- TEAEs by treatment and PT (sorted by descending frequency of PT)
- Related TEAEs by treatment and PT (sorted by descending frequency of PT)
- Serious TEAEs by treatment and PT (sorted by descending frequency of PT)
- Deaths by treatment

Detailed listings for all AEs, serious TEAEs, AEs leading to the discontinuation of study, TEAEs leading to the discontinuation of treatment, AEs leading to death, deaths and special situation will also be generated.

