### Action taken with trial drug

#### Determination of “seriousness criteria” (whether serious or not serious)

Medical history conditions, signs, symptoms, and illnesses active during the **TCH-306** Screening Period represent the medical history for participants continuing from TCH-306 into TCH 306EXT. Thus, information collected during the Screening period of TCH-306 serves as baseline for assessing AEs in TCH-306 and TCH-306EXT.

Routine titration of chronic, concomitant medications will not be considered to meet the criteria for AEs. In addition, increased IGF-1 levels requiring trial drug dose decrease (ie, IGF-1 SDS  $> 2.0$ ) will not be considered as AE. However, occurrence of clinically significant symptoms/conditions associated with increased IGF-1 levels will be considered as AE.

Investigators should use correct medical terminology/concepts when reporting AEs, or SAEs. Avoid colloquialisms and abbreviation (e.g., hypertension for elevated BP that persists and requires chronic treatment and follow-up, or increased BP for elevated BP that occurs for a limited time and does not persist or require ongoing treatment).

AEs will be documented at the maximum intensity experienced. If a previously recorded and closed AE or condition recorded as part of medical history increases in severity or frequency, it will be recorded as a new AE.

All AEs will be considered ongoing until they have completely resolved or are deemed stable or commensurate with ongoing disease processes by the investigator. At trial completion or the Early Termination Visit, all AEs should have a statement regarding resolution.

An accidental overdose is not an AE if there are no signs or symptoms. Any undesirable medical occurrence resulting from an accidental overdose is an AE and should be recorded and reported on the appropriate eCRF. Regardless of classification as an AE or not, *all* overdoses should be documented, and the participant (s) monitored. Since accidental overdoses with the trial drug could have serious clinical consequences and/or represent a compliance issue, they should be reported to the medical monitor immediately and evaluated by the Sponsor.

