10.5. MISSING DATES IN ADVERSE EVENTS

For determination of treatment-emergent adverse event (TEAE), if the start date and time of an AE are partially or completely missing, the AE will be assumed to be treatment-emergent if it cannot be definitively shown that the AE did not occur or worsen on or after the first dose in the study (worst case approach).

The following rules will be used for TEAE determination where the AE has a missing start date.

If the start time of an AE is missing, but the start date is complete, an AE will only be excluded from treatment-emergent AEs if the start day is before day of first treatment or the start day is after end of study day.

If the start time and day are missing but the start month is complete, an AE will only be excluded from treatment emergent AEs if the start month is before month of first treatment or the start month is after end month of end of study month or if the stop date/time is before the start of first treatment.

If the start day and months are missing but the start year is complete, an AE will only be excluded from treatment-emergent AEs if the start year is before year of first treatment or if the start year is after end of study year or if the stop date/time is before the start of first treatment.

If the start date is completely missing, an AE will not be excluded from treatment emergent AEs unless the stop date/time is before the start of first treatment.

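### SAP 11.11 judges treatment emergence by preferred term with no look-back limit, so read literally an event that resolved before the first extension dose and recurs on treatment is not a TEAE; the end limit also differs from SAP 10.5

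*SAP*

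**What the plan says.** **SAP 11.11 (Safety Analysis).** The unit is set at the start: "An extension period AE (classified by preferred term) will be considered as treatment emergent adverse event (TEAE"). An event occurring on extension treatment then has two ways to qualify, here called the new-event route and the worsening route: it "was not present prior to the first dose of open-label lonapegsomatropin, or it was present at the first dose" and "increased in severity during the study through 14 days after the last dose of treatment on the extension period". A separate sentence follows: "A TEAE that started on or after the first dose date of open-label lonapegsomatropin will be counted as extension period TEAE". Thirteen AE tables are then listed, and after them a set of listings that includes all AEs.

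**SAP 10.5 (Missing Dates in Adverse Events).** This section applies where the start date or time is partly or wholly missing. Its opening principle treats the event as emergent "if it cannot be definitively shown that the AE did not occur or worsen on or after the first dose in the study". With a complete date but no time, an event is excluded only if "the start day is before day of first treatment or the start day is after end of study day". Prior occurrence of the term is not tested.

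**Protocol.** Section 3 puts AEs among the endpoints for the primary objective. Section 10.3.2.1 runs AE reporting straight on from TCH-306 and stops it 2 weeks after the last injection (or at discontinuation or termination, if earlier); after that only treatment-attributed SAEs are reported. Section 10.3.3.2 says that "information collected during the Screening period of TCH-306 serves as baseline for assessing AEs in TCH-306 and TCH-306EXT", and that if a closed AE "increases in severity or frequency, it will be recorded as a new AE". Its list of required AE attributes has an onset date and no onset time.

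**The concern.** The two routes do not cover every event that starts on extension treatment. If presence is judged for the preferred term, a headache that came and went in TCH-306 was present before the first extension dose, so the new-event route is closed. It was not there at the first dose, so the worsening route is closed too. A later headache on open-label drug then has no way to qualify, even if it is more severe or serious. A mild event that happened to be ongoing at first dose and then worsened would qualify.

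Participants from TCH-306 bring a continuous AE record with them, so many terms could be blocked in this way. The flag drives most of the AE tables, the serious-TEAE listing and the repeat TEAE analysis for participants who move to the auto-injector. Two programmers could apply SAP 11.11 in good faith and produce different incidence tables.

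A secondary issue is where the emergent period ends. The 14-day limit is attached grammatically to worsening only, which leaves new events with no stated end in 11.11, while 10.5 uses an end-of-study day that it does not define.

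**Working it through.** The plan gives no figure to reproduce. The check applies each rule to the same AE histories. It assumes a complete start date with no start time, and day 100 is only an example.

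| History | 11.11 by preferred term | 11.11 per episode | 10.5, time missing |
|---|---|---|---|
| New term, day 100 | TEAE | TEAE | TEAE |
| Term resolved before first dose, recurs day 100 | **Not a TEAE** | TEAE | TEAE |
| Ongoing at first dose, worsens day 100 | TEAE | TEAE | Start-day rule excludes it; opening principle keeps it |
| New term 20 days after last dose | Depends on whether 14 days covers new events | Same | TEAE if end of study is day 28 or later |

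The second row is the point. The new-event route fails because the term was present earlier. The worsening route fails because it was not present at first dose.

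**Tables affected.** SAP 11.11 lists 13. The table of AEs leading to death and the table of deaths do not use the flag: 13 − 2 = 11.

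**Look-back.** TCH-306 treatment lasts 38 weeks (protocol 4.2). Without a Screening Visit, V8 may fall up to 8 weeks after V7 (protocol 4.1): 38 + 8 = 46 weeks. With a Screening Visit, no maximum interval from V7 is stated, so 46 weeks is not a ceiling. Commercial Switch participants have no TCH-306 history, but SAP Table 1 allows them up to 6 weeks between screening and V8, so a term could be blocked there as well.

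**Weight of one participant.** SAP section 4 gives 220 participants from TCH-306. Group sizes are not given, so these are assumed:
- equal split: 220/3 ≈ 73, and 1/73 = 1.4 percentage points;
- group of 110: 1/110 = 0.9 points;
- group of 55: 1/55 = 1.8 points.

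One participant can decide whether a term enters the table of events above 5%: 4/73 = 5.5%, but 3/73 = 4.1%.

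**End limits.** The gap between the two sections depends on what end of study means:
- V17 at 30–37 days after last dose: 30 − 14 = 16 to 37 − 14 = 23 days;
- SAP Table 2, safety follow-up/end of study, target 28 days: 28 − 14 = 14 days; at the window edges, 14 − 14 = 0 and 49 − 14 = 35 days.

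Protocol 4.4 defines end of trial by the last participant's last visit, which gives no participant-level day. These gaps also assume that the 14-day limit covers new events.

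**The case against.** The best defence is that the sentence is about an event, and that the reference to preferred term only describes coding, as the sentence before it does. On that reading a new episode was not present before first dose, so it is a TEAE and 11.11 agrees with 10.5. The follow-on sentence of 11.11 looks to start date, and 10.5 declares a worst-case approach, so both suggest this was the intent. Protocol 10.3.3.2 governs when to open a record, not treatment emergence, and it is compatible with this reading.

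This is plausible as intent, but the text does not compel it. Preferred term is named as the classifying unit, and the wording contrasts presence before the dose with presence at it. The follow-on sentence starts from an event already called a TEAE, so it either does not reach the recurrence or contradicts the two routes.

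Other parts of the defence stand. The event remains in the listing of all AEs. Injection site reactions have their own summary with no stated TEAE restriction (SAP 11.11.1). The protocol plans no formal hypothesis testing.

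Some stronger readings are tempting but not supported:
- **That 10.5 contradicts 11.11 for every recurrence.** It applies only where a start date or time is missing. The protocol's attribute list has no onset time, but the eCRF is not shown, so how often 10.5 applies is unknown.
- **That the two sections conflict over worsening of an ongoing event.** The opening principle of 10.5 keeps such events; its start-day rules merely fail to repeat it.
- **That the rule favours a particular former-treatment group.** That depends on AE histories the documents do not give.

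**Conclusion.** The definition needs correcting. Read literally it drops recurrences of any term seen and resolved before the first extension dose, and at best it is ambiguous. Up to 11 of 13 AE tables depend on the answer, for an endpoint under the primary objective. Each participant dropped lowers a term's incidence by 1.4 percentage points under the assumed equal split, or 0.9 to 1.8 points for assumed groups of 110 to 55. The total effect and its direction between groups cannot be derived. A reader might infer that safety data are lost or that the rule was meant to suppress recurrences; the documents support neither, since the listing of all AEs is retained and a per-episode intent is plausible.

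The end-limit mismatch is secondary. Routine AE collection stops at about 2 weeks and the protocol's schedule has no AE review at the final visit, so it mainly concerns late SAEs attributed to treatment. A reader might take 16 to 23 days as the size of the gap; that holds only if end of study means V17.

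**What to change.** In SAP 11.11, define a TEAE per AE record: onset on or after the first open-label dose, or ongoing at that dose and then worsened in severity. Delete the preferred-term test of prior presence. Keep preferred term only as the unit for counting each participant once, in line with protocol 9.3.5.

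State one end limit that covers both new and worsened events, and use the same limit in SAP 10.5 in place of the undefined end-of-study day. Carry the worsening principle of 10.5 into its start-day rules. If the limit is 14 days, tabulate later treatment-attributed SAEs separately so that they do not fall out of the summaries.

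The cost is one redefinition, one alignment and possibly one small table. No new assessments or data are needed, since the present rule already depends on whether severity rose after first dose. The drawback is that TEAE counts may rise, because recurrences of intermittent conditions already seen in TCH-306 would be counted.

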11.11.1. Injection Site Reactions

The number and percentage of subjects will be presented for injection site reactions and injection site reactions resulting in discontinuation of the treatment.

11.11.2. Other Adverse Events to Monitor

11.11.2.1. Clinical Laboratory Parameters

Descriptive summaries of actual (absolute) values and changes from baseline values if applicable will be presented for the following by treatment and visit:

- Chemistry: sodium, potassium, calcium, chloride, total bilirubin, alkaline phosphatase, lactate dehydrogenase (LDH), aspartate aminotransferase (AST), alanine aminotransferase (ALT), gamma glutamyl transferase (GGT), albumin, total proteins, creatinine (also eGFR calculation per MDRD equation), urea-nitrogen, uric acid, ferritin, and transferrin
- Hematology: hemoglobin, erythrocyte count, hematocrit, mean corpuscular hemoglobin (MCH), mean corpuscular volume (MCV), mean corpuscular hemoglobin concentration (MCHC), leukocytes, differential blood count of leukocytes, platelet count
- Glucose Metabolism: fasting insulin, fasting glucose, HbA1c
- Lipid Metabolism (fasting): total cholesterol, triglycerides, HDL, LDL, Lp(a) lipoprotein, free fatty acids, VLDL
- Thyroid and adrenal status: TSH, fT4, fT3, morning (06:00-10:00AM) cortisol
- Testosterone (males only)

Laboratory values will be displayed in the data listings and those that are outside the normal range will be flagged, along with corresponding normal ranges

Data listings of laboratory will also be provided, displaying details of each laboratory test for central and local laboratories separately.

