### 3. OBJECTIVES AND ENDPOINTS

| Objectives  | Endpoints  |
|---|--|
| Primary  |  |
| 

To evaluate the safety of once-weekly lonapegsomatropin in adults with GHD previously treated in trial TCH-306

  | 
Safety endpoints as measured throughout the treatment period:
 

AEs

Laboratory values

Vital signs

Immunogenicity

12-lead ECGs

Fundoscopy

  |
| Secondary  |  |
| 

To evaluate the efficacy of once-weekly lonapegsomatropin in adults with GHD

   | 
At Week 52 (as assessed by DXA):
 

Trunk percent fat

Trunk fat mass

Total body lean mass

   |

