### 5.2. EXCLUSION CRITERIA

Participants are excluded from the trial if any of the following criteria apply:

1. Diabetes mellitus if any of the following are met:
  - a. Poorly controlled diabetes, defined as HbA1C higher than 7.5% according to central laboratory at Visit 7 in trial TCH-306
  - b. Use of diabetes mellitus drugs other than metformin and/or dipeptidyl peptidase-4 (DPP-4) inhibitors
2. Active malignant disease
3. Known history of hypersensitivity and/or idiosyncrasy to the investigational product (somatropin or excipients)
4. Female who is pregnant, plans to become pregnant, or is breastfeeding

5. Female participant of childbearing potential (i.e., fertile, following menarche and until becoming post-menopausal unless permanently sterile) not willing throughout the trial to use contraceptives as required by local law or practice. Details included in Appendix 4/Section 10.4 of this protocol
6. Male participant not willing throughout the trial to use contraceptives as required by local law or practice. Details included in Appendix 4/ Section 10.4 of this protocol
7. Any disease or condition that, in the judgement of the investigator, may make the participant unlikely to comply with the requirements of the protocol or any condition that presents undue risk from the investigational product or trial procedures
8. eGFR <60 mL/min/1.73m^2 determined based on Modification of Diet in Renal Disease (MDRD) equation using serum creatinine from the central laboratory at screening
9. Hepatic transaminases (ie, AST or ALT) >3 times the upper limit of normal according to the central laboratory at screening

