## 9.3. STATISTICAL ANALYSES

### 9.3.1. General Considerations

Last assessment taken prior to the first dose of the treatment in TCH-306EXT will be used as baseline data; these include: weight, vital signs, central laboratory results, and result of DXA scan and fundoscopy.

In general, data from clinical assessments will be summarized using descriptive statistics.

Categorical data will be presented using counts and percentages of participants. Continuous variables will be presented using number of participants, mean, standard deviation (SD), standard error (SE), median, minimum, and maximum.

Details of statistical methods will be provided in the Statistical Analysis Plan.

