#### **10.3.5. Safety Monitoring**

The Sponsor will conduct an ongoing review of all trial data, with particular attention given to laboratory findings (in particular related to glucose metabolism, thyroid function and liver function), AEs, and concomitant medications. Any important safety trends or other findings considered related to the trial drug will be reported to the investigators and to regulatory authorities. In particular, the Sponsor will notify investigators and regulatory authorities of AEs that:

- Fulfill the criteria for SUSARs
- Occur at a meaningfully greater frequency than described in the current IB or Reference Safety Information.

Investigator Follow-up: Any AE that occurs during the clinical trial must be monitored and followed up until:

- It has resolved or receded
- Pathology laboratory findings have returned to normal
- Steady-state has been achieved
- It has been shown to be unrelated to the study drug and/or trial related procedure

Investigator Follow-up: Information should be elicited at all subject evaluation time points for all AEs at regular study visits. Any AE that occurs during the clinical trial should be monitored and followed up until:

- It has resolved or receded
- Pathology laboratory findings have returned to normal
- subjects are deemed stable or commensurate with ongoing disease processes
- It has been shown to be unrelated to the study drug and/or trial related procedure

or

- subject is lost to follow up or withdrawn consent or the subject has completed the study

Medical judgement should be used by the investigator to determine if attempts should be made to collect additional information for SAEs outside of regular study visits. Every effort should be made to follow all SAEs considered to be related to study drug or trial related procedure until a final outcome can be reported.

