7. ANALYSIS ENDPOINTS

7.1. SAFETY ENDPOINTS

[figure not shown]
Safety endpoints as measured throughout the 52 weeks of treatment include:

- Incidence of AEs
- Laboratory values
- Vital signs

- Immunogenicity data
- ECGs
- Fundoscopy

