11. STATISTICAL METHODS OF ANALYSES

11.1. GENERAL PRINCIPLES

In general, summaries will be performed descriptively by treatment group. Continuous, quantitative (absolute values at each time point and change from baseline if applicable) variable summaries will include the number of subjects (N) with non-missing values, mean, standard deviation (SD), standard error (SE) of the mean, median, minimum, and maximum values.

Categorical, qualitative variable summaries will include the frequency and percentage of subjects in the particular category. In general, the denominator for the percentage calculation will be based upon the total number of subjects in the study population for the cohorts.

All statistical tests will be two-sided and tested at statistical significant level of 0.05. P-values will be rounded and displayed in three decimals. If a p-value is less than 0.0001, it will be shown in tables as <0.0001. Confidence intervals will be 2-sided 95% confidence intervals, unless stated otherwise.

Unless otherwise specified, all summaries including by-visit summaries will be analyzed for the extension period (52 weeks of treatment) and for the commercial switch population, all analyses will be repeated and analyzed separately.

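### Laboratory safety, a primary endpoint, is tabulated only as continuous summaries by visit; no shift table or count of participants crossing a limit is planned

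*SAP*

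**What the plan says.** Protocol section 3 lists laboratory values under the primary objective, among "Safety endpoints as measured throughout the treatment period". SAP 7.1 repeats them: "Safety endpoints as measured throughout the 52 weeks of treatment include".

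The laboratory tables are set out in SAP 11.11.2.1: "Descriptive summaries of actual (absolute) values and changes from baseline values if applicable will be presented for the following by treatment and visit". SAP 11.1 gives the content of a continuous summary: N, mean, SD, "standard error (SE) of the mean, median, minimum, and maximum values". Protocol 9.3.1 has the same set, ending in "standard error (SE), median, minimum, and maximum".

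Individual abnormal results appear in two other places:

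- **Listings.** SAP 11.11.2.1 lists laboratory values, and "those that are outside the normal range will be flagged, along with corresponding normal ranges".
- **Adverse events.** Protocol 10.3.3.3.1 requires a laboratory result to be reported as an AE if it is symptomatic, changes trial treatment, leads to medical intervention or a change in concomitant therapy, or is clinically significant in the investigator's judgement. SAP 11.11 tabulates TEAEs by treatment, SOC and PT.

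Protocol 10.3.5 tells the sponsor to review the data "with particular attention given to laboratory findings (in particular related to glucose metabolism, thyroid function and liver function". The documents' numerical limits for HbA1c (above 7.5%), eGFR (below 60 mL/min/1.73m²) and liver enzymes ("Hepatic transaminases (ie, AST or ALT) >3 times the upper limit of normal according to the central laboratory at screening") are all exclusion criteria in Protocol 5.2.

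**The concern.** Laboratory harm usually shows in a few participants, not in a shift of the whole group. A table of means, SDs and medians by visit describes the group. The minimum and maximum show one extreme value per group and visit. They do not say how many participants crossed a limit, or whether the extreme participant was already beyond it at baseline.

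The number of participants who newly became abnormal on treatment, by prior treatment group, is the usual question for a laboratory safety endpoint, and no planned laboratory table answers it. The SAP does count participants elsewhere: injection site reactions get n (%) (SAP 11.11.1), and antibodies get incidence by treatment-emergent and treatment-boosted type (SAP 11.11.2.2). Glucose, thyroid and liver results, which the protocol singles out, get no such count.

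The by-visit tables can also lose abnormal values. Protocol 8.2.4 allows repeat and unscheduled samples for safety reasons. SAP 10.8 maps each to the nearest scheduled visit and keeps only the record closest to the target day. A safety sample further from the target than the scheduled one is left out of the table, including its minimum and maximum, and survives only in the listing.

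At stake is how the primary safety conclusion on laboratory values is supported. Summaries showing little mean change could stand alongside a handful of new abnormalities whose frequency is nowhere stated.

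**Working it through.** The plan has no figure to reproduce: it has no sample-size calculation, and no alpha or power attached to laboratory values. The check has three parts.

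**1. Where an abnormal laboratory result would appear**

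| Output | What it shows | What it leaves out |
|---|---|---|
| By-visit summary (SAP 11.11.2.1, 11.1) | Group distribution; one minimum and one maximum | How many crossed; baseline status of the extreme participant |
| Listing (SAP 11.11.2.1) | Every value, flagged if outside the normal range | Incidence by group; any limit other than the normal range |
| TEAE tables (Protocol 10.3.3.3.1; SAP 11.11) | Incidence of abnormalities reported as AEs | Asymptomatic results that change no treatment and are not judged clinically significant |

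**2. The visit-window rule, by example**

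In SAP Table 2, Week 28 has target X1+196 and window X1+158 to X1+231. Suppose the scheduled sample falls on X1+198 and an abnormal unscheduled sample on X1+215. The distances from target are 2 and 19 days. The scheduled value is kept and the abnormal one does not enter the Week 28 table.

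**3. How far a few crossers move the summary**

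From the documents: 220 participants from TCH-306 and 13 commercial-switch participants (SAP section 4).

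Assumed, not in the documents: three prior arms of equal size, 220/3 ≈ 73; 4 participants with an HbA1c rise of 1.5 points; a background SD of change of 0.3 to 0.5 around zero in everyone.

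- Shift in the arm mean: 4 × 1.5/73 = 0.082.
- Variance added by the crossers, with p = 4/73 = 0.0548: 1.5² × p(1 − p) = 2.25 × 0.0518 = 0.1165.
- Background SD 0.3: total SD = √(0.09 + 0.1165) = 0.454; SE = 0.454/√73 = 0.053; 95% half-width = 1.96 × 0.053 = 0.10.
- Background SD 0.5: total SD = √(0.25 + 0.1165) = 0.605; SE = 0.605/√73 = 0.071; half-width = 0.14.

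The shift of 0.08 is therefore inside the interval at both ends: 0.082/0.053 = 1.5 SE and 0.082/0.071 = 1.2 SE.

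The background spread matters. If the other 69 participants did not change at all, the SD would be √0.1165 = 0.34, the SE 0.34/√73 = 0.040, and the shift about 2 SE. That case is unrealistic, but it shows that the mean is not always blind to a few crossers.

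What a count would report:

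- 4/73 = 5.5%, exact (Clopper-Pearson) 95% CI 1.5 to 13.4.
- 3/73 = 4.1%, CI 0.9 to 11.5.
- 0/220: upper limit of the two-sided exact 95% CI 1.7%.
- 0/13 (commercial switch): upper limit 24.7%.

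A count gives both a rate and its precision, including when nobody crosses.

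**The case against.** The strongest reply is that crossers will be seen. The maximum value and maximum change are tabulated at six post-baseline safety-laboratory visits (V9 and V11 to V15 in the schedule of activities), so a 1.5-point HbA1c rise at a scheduled visit would show as the maximum change unless someone rose further. Listings flag every out-of-range value. Results that are symptomatic, acted on or judged clinically significant must be reported as AEs and reach the TEAE tables; Protocol 10.3.3.3 even gives worsening type 2 diabetes as an example of a reportable event. Reporting is descriptive, with no hypothesis testing (Protocol 9.1), and extra tables could be produced later.

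Much of this stands. A reader might infer that laboratory safety is reported by means alone, or that threshold crossers would go unseen. The documents do not support either reading: SAP 11.1 adds median, minimum and maximum, and the listings and AE rules expose individuals. A reader might also take the limits in Protocol 5.2 as on-treatment safety limits that the SAP failed to apply. They are entry criteria only, and Protocol 10.3.5 does not name renal function.

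The reply does not supply a count. A listing gives no incidence by group and flags the normal range only. A maximum is one person and can miss an unscheduled sample. The AE route depends partly on investigator judgement, in an open-label trial without a data monitoring committee (Protocol 10.1.5). Where a diagnosis applies, Protocol 10.3.3.3.1 records it in place of the laboratory abnormality, so one laboratory signal can be spread over several preferred terms. Tables added after the data are seen would lack limits fixed in advance.

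**Conclusion.** The concern holds as a gap in tabulation. Abnormal laboratory values will be visible one by one, but nothing planned in the laboratory section counts the participants who newly cross a limit, and the by-visit tables can omit abnormal unscheduled samples. That section shows no redaction; the conclusion rests on the visible text of the SAP, parts of which are blacked out elsewhere.

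Under the stated assumptions, a 5.5% rate of sizeable HbA1c rises in one arm moves its mean by 0.08 points against a 95% half-width of about 0.10 to 0.14. The arm size, the rise and the background SD are illustrative, so the figures show the order of magnitude and do not predict results. The point matters less for the commercial-switch group, where 13 participants can be read from a listing.

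This should be changed before the analysis. It affects how clearly the primary endpoint is reported; it does not affect trial conduct or error control.

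**What to change.** Add to SAP 11.11.2.1, by prior treatment group and pooled, with the commercial-switch group separate as in SAP 11.1:

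1. Low/normal/high shift tables from baseline (as defined in SAP 8.5) to the worst on-treatment value. State that all on-treatment samples count, including unscheduled ones, so that the SAP 10.8 window rule does not apply to these tables. Say whether local-laboratory results are included.
2. The number and percentage of participants newly beyond a prespecified reporting limit at any time on treatment, among those not beyond it at baseline. Cover glucose metabolism, liver and thyroid, which Protocol 10.3.5 names, and eGFR. Show the denominator for each parameter.

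The sponsor should specify the limits before database lock. The entry cut-offs in Protocol 5.2 are possible choices for HbA1c, AST/ALT and eGFR, and the laboratory normal range for thyroid tests. These would be reporting limits only and would change no clinical rule.

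The cost is a few more programmed tables from central-laboratory data already collected. No visit, sample or procedure changes.
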